#### 4.5. Sample size calculation

##### Considerations for calculation of the sample

Since there are no study examining the effect of screening with the strategies proposed in our trial on CRC-caused mortality, the calculation of the sample in this case must be based on hypothetical studies of cost-effectiveness that analyse the expected reduction in risk of mortality with biennial FIT or colonoscopy every 10 years. Furthermore, the calculation should be adjusted, when possible, to the local conditions where the strategies are to be implemented. In that sense, it is important to note that no study on this subject have yet been published in Spain.

Recently, the Evaluation and Planning Unit of the Canary Islands Health Service has conducted a study of this type based on real data for sensitivity and specificity of the tests in our setting. For a hypothetical population of 100,000 asymptomatic individuals aged 50, the estimated mortality reduction brought about by FIT is 51% and involves a cost of € 2,101/QALY. For the strategy of colonoscopy, the estimate is a reduction in mortality of 75% at a cost of € 2,188/QALY.

With an alpha risk of 0.025 and a beta risk of 0.10 using one-sided test of proportions, 27,749 subjects are required in each arm of the clinical trial (total: 55,498) accepting a non-inferiority condition if the absolute difference was below 1.6% in the CRC-specific mortality rate at 10 years according to the intention to screen analysis and with an expected overall compliance of 30%.

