#### Estimates of recruitment by Autonomous Region

According to the established sample size, the number of individuals to be recruited in each Autonomous Region is 6,937.

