#### Secondary end points:

1. *Participation, detection rate, diagnostic yield and complication rate at the completion of the first round and at the end of study (10 years)*

Definitions of these four key outcomes are as follows:

- Participation: number of participating individuals (i.e. individuals who completed colonoscopy in the colonoscopy group and individuals who returned the test in the FIT arm) relative to the number of eligible individuals.
- Detection rate: number of true positives relative to the number of participating individuals.
- Diagnostic yield: number of true positives relative to the number of eligible individuals.
- Complication rate: number of major complications (i.e. perforation, postpolypectomy bleeding requiring hospitalization, and cardiovascular/pulmonary complications requiring medical management) relative to the number of participating individuals.

Differences in these four key outcomes between both strategies will be established by logistic regression analysis, adjusted by age, gender and participating centre, and reported as odds ratios (OR) with 95% CI.

*2. Overall survival at the end of study (10 years)*

*3. CRC incidence at the end of study (10 years and 15 years)*

*4. Cost-effectiveness analysis*

Cost-effectiveness will be studied with a Markov's model at the completion of study. Results will be reported in terms of quality-adjusted life years (QALY).

*5. Analysis of factors influencing participation in the study*

Factors associated with participation at the completion of first round and at the end of study (10 years) in each screening strategies will be analysed by logistic regression analysis and results reported as OR with 95% CI. Parameters analysed will include demographics, personal and familial characteristics, socio-economic status, etc.

*6. Number needed to screen to detect a colorectal cancer*

The number needed to screen to detect a CRC will be calculated using the inverse of risk (i.e. the number of participants receiving a given screening modality divided by the number of positive cases in that given modality), with 95% CI computed using the inverse of the binomial standard approximation.

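### The stated interval for the number needed to screen, read as inverted Wald limits, sits too high at both ends: by 3 to 6% at 25 to 42 cancers, more at lower counts

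*Combined protocol and SAP*

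**What the plan says.** Section 7 (SAP), Secondary end points, item 6, defines the number needed to screen as "the number of participants receiving a given screening modality divided by the number of positive cases in that given modality". For the precision of that figure, the same item specifies an interval as follows: "with 95% CI computed using the inverse of the binomial standard approximation". The item does not use the word Wald, give a formula, offer another method for small counts, or say what to report when no cancer is found. It reports by modality and mentions no screening round, region or subgroup.

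The documents state no expected number of cancers and no cancer detection rate. For a denominator, section 4.5 gives the arm size: "27,749 subjects are required in each arm of the clinical trial (total: 55,498". The participation assumption stands later in that section, where the size is said to be calculated "with an expected overall compliance of 30" per cent.

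**The concern.** Cancer found at screening is a rare outcome. For a rare proportion the Wald interval is symmetric around an estimate whose sampling distribution is skewed, so both of its limits tend to lie too low. Inverting turns this into an interval for the number needed to screen whose two limits both lie too high. Screening then looks less productive than the data support.

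The shift grows as the number of cancers falls. When two modalities are set side by side, the one with fewer cancers has its interval moved further, and that could colour an informal comparison.

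**Working it through.** **Inputs.** Subjects per arm: 27,749 (section 4.5). Compliance: 30% (section 4.5). Participants: 27,749 × 0.30 = 8,324.7, taken as n = 8,325. Using this for a modality is an assumption, since cross-over would change the number who receive each test. The cancer count k is also an assumption, varied from 8 to 42 (detection risk about 0.1% to 0.5%). The plan has no figure of its own to reproduce.

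**Formulas.** With p = k/n, Wald limits are p ± 1.96·√(p(1−p)/n). The interval for the number needed to screen is (1/upper, 1/lower). Clopper-Pearson (exact) and Wilson (score) limits are inverted in the same way.

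**Example, k = 25.** p = 25/8,325 = 0.003003 and SE = √(0.003003 × 0.996997/8,325) = 0.000600. The Wald limits are 0.001828 and 0.004178, which invert to 239 and 547. Exact limits invert to 226 and 514. So 547/514 = 1.06 and 239/226 = 1.06.

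| Cancers | Inverted Wald | Inverted exact | Inverted Wilson | Upper limit, Wald over exact | Lower limit, Wald over exact |
|---|---|---|---|---|---|
| 42 | 152–284 | 147–275 | 147–268 | +3% | +4% |
| 25 | 239–547 | 226–514 | 226–491 | +6% | +6% |
| 15 | 369–1,123 | 337–991 | 337–916 | +13% | +9% |
| 8 | 615–3,385 | 528–2,410 | 528–2,053 | +40% | +16% |

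Against Wilson, the upper-limit excess is larger: 6%, 11%, 23% and 65% in the same order.

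**Where the misses fall.** On the count scale the Wald limits are close to k ± 1.96√k.
- Expected 8 cancers: a count of 4 gives an upper limit of 4 + 3.92 = 7.92, below 8. Any count of 4 or fewer therefore puts the lower limit of the number needed to screen above the truth; the Poisson probability is 10.0%. The opposite miss needs 16 or more cancers (16 − 7.84 = 8.16) and has probability 0.8%.
- Expected 25 cancers: 3.8% and 1.5%.
- Expected 42 cancers: 4.8% and 1.6%.

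Each tail should be 2.5%. The lower limit is the one that misses too often. The upper limit misses too rarely, which means it is too wide.

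**When the upper limit turns negative.** The Wald lower limit is below zero when k < 1.96²(1−p), about 3.84, so for 1, 2 or 3 cancers. At k = 3 the inverted limit is −21,122, against 13,455 exact. At k = 4 it is positive but useless (102,760). With n = 8,325 the probability of 3 or fewer cancers is 3.4% at a 0.1% detection risk, 0.005% at 0.2% and about 4 in 100 million at 0.3%.

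**A small subset, for contrast.** Section 4.5 says "the number of individuals to be recruited in each Autonomous Region is 6,937". One region's arm would have 6,937/2 × 0.30 = about 1,040 participants. The probability of 3 or fewer cancers would then be 84% at 0.2% and 40% at 0.4%.

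**The case against.** **The method is inferred.** This stands. The wording could also mean a normal approximation for 1/p itself (delta method), which errs in the opposite direction: at 25 cancers it gives 203–463 against 226–514 exact, and at 8 cancers 320–1,761 against 528–2,410. Inverted Wald limits remain the natural reading, since the rest of the SAP builds its risk intervals on the normal approximation. That two readings err in opposite directions is itself a reason to name the method.

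**The effect is small at moderate counts.** This also stands. An interval of 152–284 in place of 147–275 would change no conclusion. Total Wald coverage is near nominal (about 94.7 to 95.0%) at detection risks from 0.3% to 1%; what remains there is the imbalance between the tails.

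**The number needed to screen decides nothing.** Correct. It is the last of six secondary end points, does not appear among the objectives in section 3, and has no test or margin attached. Item 1 compares detection rate and diagnostic yield by adjusted logistic regression.

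**Stronger readings to avoid.** A reader might infer that the trial's interval will come out negative, or that later FIT rounds or single regions will show this. The documents do not support either: item 6 plans no reporting by round or region, and a negative limit needs three or fewer cancers in a whole modality. A reader might also take the inflated upper limit to be where coverage fails, but the excess misses are at the lower limit.

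**Conclusion.** The point holds as a minor one. If item 6 means inverted Wald limits, both limits of the number needed to screen are too high: by 3 to 6% at 25 to 42 cancers, rising at 8 cancers to 40% for the upper limit and 16% for the lower. The lower limit lies above the truth about 10% of the time at an expected 8 cancers and 4 to 5% at 25 to 42. A negative upper limit would matter only if the figure were also reported for small subsets, which the SAP does not state.

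This rests on the Wald reading, on about 8,325 participants per modality, and on cancer counts that the documents do not supply. The primary non-inferiority comparison is not affected.

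**What to change.** In item 6, replace the standard approximation with inverted Wilson (score) limits for the detection risk, and name that one method. Clopper-Pearson is an acceptable alternative, slightly conservative: it holds each tail at or below 2.5%, whereas Wilson at very low counts can err modestly the other way (at a 0.1% detection risk, tails of 1.1% and 4.5%, total coverage 94.5% against 91.2% for Wald). The two differ at small counts, for example upper limits of 2,053 and 2,410 at 8 cancers, so the choice should be made before the counts are seen.

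Add a rule for zero cases: the point estimate is undefined, so report only the lower bound of the number needed to screen. With Wilson limits that bound is (n + 3.84)/3.84, or about 2,170 at n = 8,325.

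The cost is one phrase and one sentence in the SAP, with no change to data, design or other analyses.

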## 8. CHRONOGRAM

The study will be developed according to the following chronogram:

- Initial meeting: October 28th, 2008
- Formative meeting for data-collectors and other auxiliary staff: December 12th, 2008
- Informative campaign launched by the Spanish Alliance for CRC Prevention and involving national and local media: from November 2008 to March 2009
- Recruitment period will be initiated in June 2009
- Quality Committee meetings will be held during the first round according to the following calendar:
  - June 12th, 2009
  - December 11th, 2009
  - June 11th, 2010
  - December 10th, 2010
- First round of screening will be finished in June 2011
- First follow-up meeting (first-round interim analysis): July 2011
- Other follow-up meetings will be held regularly during the study period, in a biennial basis (date will be announced properly)
- Other Quality Committee meetings will be held regularly during the study period, in a annual basis (date will be announced properly)
- Completion of the study: December 2021
- Analyses of main end point results (i.e. CRC mortality and incidence and any-cause mortality at 10 years): June 2024
- Follow-up conference calls among members of the Executive Committee will be held periodically, every four months, during the study period.

## **9. ETHICAL QUESTIONS**

The study will respect the Helsinki declaration, the European Council Human Rights and Biomedicine, and the UNESCO Universal Declaration about human genome and human rights. Moreover, the study will fulfil established requisites about biomedical investigation, data protection and bioethics of the Spanish law.

People included in this study will receive appropriate information about objective, methodology and study procedures. Thereafter, they will provide written informed consent for participating in the study.

This study receives the approval of the Ethics Committee of Clinical Investigation and the Research Committee of every of the participant hospitals.

## 10. RESEARCH PROJECT TEAM

All the investigators will be grouped together under the name of “*Grupo Cooperativo para el Cribado del Cáncer Colorrectal en España*” or “COLONPREV study”.

Every LSO, hospital and Heath Centre will designate a responsible. Among them, a **Local Coordination Committee** will be chosen and a **Coordinator** will be named.

Local Coordinators of all Autonomous Regions will constitute the **Executive Committee**. This committee will name the **National Coordinators** and will establish publication criteria for the study.

In the heading of the publications related to the main and secondary objectives of the study will appear, at least, the National Coordinators, members of the Executive Committee, responsible of every participant hospital, LSO and Health Centre, and the methodological assessors, followed by “on behalf of the *Grupo Cooperativo para el Cribado del Cáncer Colorrectal en España*” or “on behalf of COLONPREV study investigators”. All other investigators will appear in a supplementary note at the end of the publication.

